## 5.6. Efficacy Endpoints

All efficacy endpoints will be analyzed by randomized treatment group for all mITT participants in the full analysis set, unless otherwise specified.

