16.2. Efficacy

16.2.1. Analysis Population

The primary efficacy analyses will be conducted in the modified intent-to-treat population, which is defined as participants who are randomized and treated and have at least 1 centralized read of contusion volume from an NCCT or MRI scan acquired between 12 hours after the initiation of study treatment and by the Hour 96 Visit or prior to DC, IPH evacuation, or CMO, if performed before the Hour 96 visit.

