### 3.6.1. Full Analysis Set

The full analysis set, i.e., the modified intention-to-treat (mITT) participants, will include all the participants who are randomized, receive any study drug (BIIB093 3 mg/day, BIIB093 5 mg/day or the matching placebo), and have at least one final read per central review of contusion volume from an NCCT or MRI scan acquired between 10 hours after the initiation of study drug infusion and the Hour 96 visit or NSx or CMO (if earlier). In efficacy analyses performed on the full analysis set (mITT participants), participants will be analyzed according to the randomized treatment group (see [Section 3.2.1](#) for the definition).

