### 3.6.2. Per-Protocol Analysis Set

The per-protocol analysis set will include mITT participants who have no protocol violations described below. In analyses performed on the per-protocol analysis set, participants will be analyzed according to actual treatment group (see [Section 3.2.2](#) for the definition). The detailed

definitions of protocol deviations, listed below, will be determined and documented prior to the Day 4 administrative database lock.

- Violation of eligibility criteria
  - Time to infusion post injury/last known normal (LKN) is more than 10 hours
  - Baseline contusion volume per investigator is  $\leq$  3 mL or missing
  - Baseline GCS is outside the range of 5-15
- Early discontinuation of treatment
  - Infusion is discontinued within 12 hours from the initiation of study drug infusion

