#### 5.1.4. Missing Values for GOS-E

GOS-E at [REDACTED] 180 will be analyzed as a 7-category ordinal scale (1/2, 3, 4, 5, 6, 7, 8). Multiple imputation will be used to account for missing values for GOS-E. Death and vegetative state are scored as 1 and 2 in GOS-E and therefore no missing GOS-E values are expected due to death or vegetative state. Missing GOS-E values due to reasons other than death or vegetative state will be imputed based on a linear model performed on the GOS-E scores leveraging the information of the patient at other time points as well as the time patterns of all other participants. The model will include treatment as a classification variable and other covariates: GOS-E score at the previous timepoint, region (North America and RoW), age ( $\leq 70$ ,  $> 70$  years), baseline GCS (5-8, 9-12, 13-15), baseline contusion volume per investigator ( $> 3$  to 10 mL vs  $> 10$  mL). Imputed values will be rounded to the closest valid GOS-E score, 100 imputations will be conducted with random seed pre-specified, and each imputation will result in a complete dataset for all mITT participants.

The missing data pattern will be evaluated including reasons for missingness, missing data by randomized treatment group and visit, and potential covariates associated with missingness. Sensitivity analyses will be planned to evaluate the robustness of the results from the main analysis of GOS-E.

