### 5.6.3. Secondary Efficacy Endpoints

#### GOS-E at Day 180

GOS-E will be assessed as a 7-category ordinal scale (1/2, 3, 4, 5, 6, 7, 8) at discharge, Day 30, Day 90, and Day 180.

- GOS-E at Day 180 will be analyzed by randomized treatment based on observed data for the full analysis set using ordinal logistic regression adjusting for covariates specified in Section [5.6.1](#).

- Dichotomized GOS-E (0-4 versus 5-8) at Day 180 will be analyzed using binary logistic regression adjusting for covariates specified in Section [5.6.1](#).
- Multiple imputation for missing GOS-E values at Day 180 will be conducted as specified in Section [5.1](#). The analysis results from imputed datasets will be combined for inference using Rubin's rule.
- Descriptive statistics for GOS-E scores will be summarized by visit (see Section [5.1](#)).

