### **mRS at Day 90**

mRS will be assessed at Day 90 and Day 180 as a 5-category ordinal scale (0/1, 2, 3, 4, 5/6).

- mRS at Day 90 will be analyzed in the final database for the full analysis set using ordinal logistic regression based on observed data adjusting for covariates specified in Section [5.6.1](#).
- Dichotomized mRS (0-2 versus 3-6) at Day 90 will be analyzed using binary logistic regression adjusting for covariates specified in Section [5.6.1](#).

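### GOS-E at Day 180 and mRS at Day 90 are analysed in a set that requires a post-dose scan, a post-randomization condition these endpoints do not need

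*SAP*

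**What the plan says.** The general rule in SAP 5.6 is: "All efficacy endpoints will be analyzed by randomized treatment group for all mITT participants in the full analysis set, unless otherwise specified". The endpoint text repeats it. For GOS-E, SAP 5.6.3 says "GOS-E at Day 180 will be analyzed by randomized treatment based on observed data for the full analysis set using ordinal logistic regression"; for mRS, "mRS at Day 90 will be analyzed in the final database for the full analysis set". Delayed intubation is on the same set in SAP 5.6.3. Table 3 lists mITT and per-protocol for all three, and SAP 4.3 uses the full analysis set for the final analysis.

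SAP 3.6.1 defines that set as randomized, dosed, and with at least one final central read of a scan "acquired between 10 hours after the initiation of study drug infusion and the Hour 96 visit or NSx or CMO (if earlier". Protocol 16.2.1 opens the window at 12 hours and closes it differently: "or prior to DC, IPH evacuation, or CMO, if performed before the Hour 96 visit".

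The one visible exception is survival, analysed in all randomized participants (SAP 3.6, 5.6.1 and 5.6.3; Protocol 16.2.2.3). The Version 2 amendment rationale explains that this keeps survival information whether or not admissible images exist, and says that the other endpoints use mITT. So the choice is deliberate.

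**The concern.** Having a qualifying scan is settled after randomization and dosing. A volume change cannot be computed without a scan, so the condition makes sense for imaging endpoints. GOS-E and mRS can be scored without one. A participant who dies or has a procedure before a qualifying scan leaves the functional comparison although the outcome is known. If such participants differ between arms, in outcome or in number with unusual outcomes, the comparison is no longer the randomized one. A drug that limits contusion expansion could itself change who has early surgery, moves to comfort measures or dies early. The Version 3 rationale prefers Day 180 GOS-E because it is the registrational endpoint in TBI studies, and the trial informs Phase 3 planning.

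**Working it through.** **1. Do these endpoints need the scan?**
- Follow-up: Protocol 7.2 follows all randomized participants for 180 days unless consent is withdrawn.
- Death: GOS-E scores it as 1 (SAP 5.1.4), and the 5/6 category of mRS includes it.
- Covariate: SAP 5.6.1 adjusts for baseline contusion volume by central review, not for a follow-up volume. The survival model already needs that value for all randomized participants.

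**2. Does anything visible restore those excluded?**
- Imputation: no. In SAP 5.1.4, "each imputation will result in a complete dataset for all mITT participants". mRS is not imputed (SAP 5.1.5).
- Per-protocol: no. In SAP 3.6.2, "The per-protocol analysis set will include mITT participants who have no protocol violations described below".
- Baseline tables (SAP 5.3), death counts (5.7.3) and survival (5.6.3) cover all randomized participants, but give no GOS-E or mRS results.
- SAP 5.1.4 also says "Sensitivity analyses will be planned to evaluate the robustness of the results from the main analysis of GOS-E", without naming a set or method.

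**3. Who is excluded?**
- Under either document: participants never dosed, and those who die or reach comfort measures, decompressive craniectomy (DC) or intraparenchymal hematoma (IPH) evacuation without a qualifying scan.
- Under the SAP wording only: participants with other neurosurgery before a qualifying scan. SAP 3.6.1 closes the window at NSx, and SAP 5.5.3 counts craniotomy as NSx. Version 3 allows surgery for extra-axial injuries, and Protocol Table 2, footnote 5, expects no scan for other NSx. The first scheduled post-dose NCCT is at Hour 24 ± 6, that is Hour 18 to 30. Protocol 16.2.1 names only DC, IPH evacuation and comfort measures, so there this route does not exist.

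**4. How large could the effect be?** The plan's only power figure is for the primary endpoint, and it reproduces: 15/(29 × √(2/80)) = 3.27; 3.27 − 1.96 = 1.31; power 90.5%, against about 90% stated. It is not in dispute. The documents give no mITT size and no GOS-E power, so the following counts are assumptions.

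Take 80 per arm, 32 unfavourable (GOS-E 1 to 4) and 48 favourable in each, so the true odds ratio (OR, active to placebo, for unfavourable) is 1.00. Exclude a active and b placebo participants. If all are unfavourable, OR = (32 − a)/(32 − b). The standard error (SE) of log OR is √(sum of 1/cell).

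| Excluded (active, placebo) | Outcome of excluded | Remaining unfavourable | OR | SE | log OR/SE |
|---|---|---|---|---|---|
| 4, 4 | all unfavourable | 28/76 vs 28/76 | 1.00 | 0.34 | 0 |
| 1, 3 | all unfavourable | 31/79 vs 29/77 | 1.07 | 0.33 | 0.2 |
| 2, 6 | all unfavourable | 30/78 vs 26/74 | 1.15 | 0.34 | 0.4 |
| 2, 6 | half unfavourable | 31/78 vs 29/74 | 1.02 | 0.33 | under 0.1 |
| 2, 6 | 40% unfavourable, as the rest | 31.2/78 vs 29.6/74 | 1.00 | – | 0 |

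For the third row: (30/48)/(26/48) = 1.154; SE = √(1/30 + 1/48 + 1/26 + 1/48) = 0.337; 95% CI 0.60 to 2.23. Swapping the arms gives 0.87. With 40 of 80 unfavourable instead, the same split gives 38/34 = 1.12, or 0.89 when swapped.

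A 7-category proportional-odds fit, with assumed counts per arm of 16, 10, 6, 10, 12, 12, 14 and the 2 and 6 all removed from the worst category, gives 1.15 or 0.87, SE 0.28, about 0.5 SE. With the exclusions spread over categories it gives 1.01 or 0.99.

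**The case against.** The best defence is that few participants will be excluded and the effect is small. Eligibility removes those with an indication for immediate IPH evacuation or DC and those likely to move to comfort measures. Scans are requested before those events, and SOC scans collected by the imaging CRO up to the cut-off also count (SAP Appendix 1). The endpoints are secondary, in a Phase 2 trial that SAP 5.6.1 says is not powered for a moderate GOS-E effect. All of this stands, and it sets the severity.

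A second argument is that the trial is double-blind with blinded readers, so unequal exclusions are chance and already part of the sampling error. That holds if treatment does not affect who gets a qualifying scan. Blinding cannot guarantee it, because an active drug could change early surgery, comfort measures or death.

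Three stronger readings are tempting, and the documents do not support them:
- That the SAP has no analysis at all outside mITT. Text is blacked out in SAP 5.1 straight after the sentence on per-protocol supplementary analyses, and contents entries are redacted after 3.6.3. SAP 5.2 uses a follow-up set with no visible definition, and the GOS-E sensitivity analyses are unspecified. The statement must be limited to visible text.
- That participants with extra-axial surgery are necessarily lost. That follows only from the NSx wording in SAP 3.6.1. Protocol 16.2.1 and the primary estimand in SAP 5.6.2 name DC, IPH evacuation and comfort measures.
- That mITT for functional outcomes was an oversight. The Version 2 rationale shows a choice, although it gives no reason why these outcomes need a scan.

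**Conclusion.** The point holds as a minor improvement. The visible plan puts a post-randomization scan condition on GOS-E, mRS and delayed intubation, which do not need it, and its own argument for survival applies equally to scales that score death. The size rests on assumed counts: with 8 of 160 excluded, split 2 and 6 and all unfavourable, a null odds ratio moves by about 0.4 SE in either direction. Balanced exclusions, or exclusions with the same outcome mix as the rest, move it not at all. A reader might infer that the GOS-E result will be biased or the trial undermined; neither the number excluded nor any difference between arms can be known from the documents, so that does not follow.

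**What to change.** In SAP 5.6, 5.6.3 and Table 3:
- Make all randomized participants, by randomized group, the main set for GOS-E at Day 180 and mRS at Day 90, matching the survival rule. At the least, use all randomized and dosed, accepting that dosing is also a post-randomization condition. Consider the same for delayed intubation.
- Run the SAP 5.1.4 imputation on that set. Its model uses the previous GOS-E, and GOS-E starts at discharge, so where no earlier score exists impute the visits in sequence. Leave mRS on observed data, with death scored 6.
- If all randomized are used, anchor visit days at randomization for those never dosed, because SAP 3.1 sets Study Day 1 at infusion start.
- Keep mITT and per-protocol as supplementary for these endpoints, and keep mITT for imaging endpoints.
- Report by arm the number outside mITT, with reasons.

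The cost is SAP text, a few outputs and a little more imputed data. Central baseline reads are needed for participants outside mITT; scans of enrolled participants already go to the imaging core laboratory (Protocol 19.1.5). No new data collection is needed.

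Two separate points: the Table 3 row for time to death should say all randomized in place of mITT, keeping per-protocol as supplementary. The differing scan windows in SAP 3.6.1 and Protocol 16.2.1 should be reconciled in their own right.

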### 5.6.1. General Analysis Methods for Efficacy Endpoints

All endpoint models (binary logistic regression, ordinal logistic regression, Cox model, and analysis of covariance) below will regress the outcome on the randomized treatment group, comparing the BIIB093 combined with placebo groups, adjusting for all the IRT stratification factors at randomization (see [Section 3.5.1](#)), baseline contusion volume per the central review and baseline GCS.

Analysis of covariance (ANCOVA) will be performed to compare the change in total contusion volume (primary analysis), change in absolute hematoma volume, the change in absolute edema volume, [REDACTED] from baseline in the main analysis comparing the BIIB093 combined with placebo groups. The least square (LS) mean difference with the corresponding 2-sided 95% CI and p-values for the treatment group will be provided.

Binary logistic regression will be used for binary outcomes comparing the BIIB093 combined with placebo groups. Odds ratio, the corresponding 2-sided 95% confidence interval (CI) and p-value will be reported for the treatment group.

Ordinal logistic regression (proportional odds model) will be used for GOS-E as a 7-category ordinal scale (1/2, 3, 4, 5, 6, 7, 8) and for mRS as a 5-category ordinal scale (0/1, 2, 3, 4, 5/6) at Day 90 and 180. Odds ratio, the corresponding 2-sided 95% CI and p-value for the treatment group will be reported.

The proportional odds ratio assumption will be tested using likelihood ratio test based on observed data. In the case the assumption does not hold (p-value < 0.05) or non-convergence, the Mann-Whitney test will be used as the primary inference and the source of non-proportionality or non-convergence will be investigated. Following the Mann-Whitney test, dichotomized analysis will be conducted to assess the treatment effects.

The Cox proportional hazard model will be used to assess the treatment effect on overall survival at Day 90 for all randomized participants. Hazard ratio, 2-sided 95% CI as well as the p-value for the treatment group will be reported. Kaplan-Meier curves will be presented by randomized treatment group, and Greenwood's formula will be used to calculate the standard error of the Kaplan-Meier estimates.

Multiplicity will be not be adjusted for the tests of the primary and secondary endpoints, since the current study sample size is not powered for a moderate treatment effect on GOS-E.

To explore the exposure-response relation of different BIIB093 doses, similar efficacy endpoint models will be used for analyzing the two active dose arms separately (BIIB093 3 mg/day vs. BIIB093 5 mg/day vs. placebo). The results of the exposure-response analysis will report point estimate of the treatment effect (odds ratio, hazard ratio, or least-square mean difference) and the corresponding 2-sided 95% CIs. No p-values for the exposure-response analysis will be reported.

Table 3: Main Analyses for Efficacy Endpoints

Endpoints	Analysis method	Analysis Population	SAP Section
Primary endpoint			
Change in total contusion volume as measured by brain imaging from baseline to 96 hours or prior to DC, IPH evacuation or CMO if these procedures occur before 96 hours per the central review	Analysis of Variance (ANCOVA)	mITT per-protocol	5.6.2

Secondary endpoints			
GOS-E at Day 180	Ordinal logistic regression with multiple imputation	mITT per-protocol	5.6.3
mRS as 5-category ordinal scale (0/1, 2, 3, 4, 5/6) at Day 90	Ordinal logistic regression	mITT per-protocol	5.6.3
mRS as 2-category ordinal scale (0-2 vs 3-6) at Day 90	Binary logistic regression	mITT per-protocol	5.6.3
Proportion of participants requiring delayed intubation	Binary logistic regression	mITT per-protocol	5.6.3
Change in total contusion volume from baseline to 24 hours or prior to DC, IPH evacuation or CMO if these procedures occur before 24 hours per the central review	Analysis of Variance (ANCOVA)	mITT per-protocol	5.6.3
Change in absolute hematoma volume from baseline to 24 hours	Analysis of Variance (ANCOVA)	mITT per-protocol	5.6.3
Change in absolute edema volume from baseline to 96 hours	Analysis of Variance (ANCOVA)	mITT per-protocol	5.6.3
Time to all-cause death through day 90	Cox proportional hazards regression model	mITT per-protocol	5.6.3

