16.2.2.2. Analysis of the Primary Endpoint

Primary analysis of the primary endpoint will compare BIIB093 (3 mg/day or 5 mg/day) and placebo groups using an ANCOVA (analysis of covariance) model, adjusting for covariates including all the stratification factors at randomization, 96 hours imaging modality (MRI vs NCCT) and baseline contusion volume per the central read. Multiple imputation will be used to account for the missing values for Hour 96.

Sensitivity analyses for the assumptions will be performed to evaluate the impact of analysis sets, the impact of missing data, and the intercurrent event handling. Details will be specified in the SAP.

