Rationale: According to the current protocol definition of expansion, the pooled blinded proportion of patients meeting the contusion expansion criteria appeared to be very high, particularly for participants with MRI scans at 96 hours. This high proportion was significantly greater than the assumed 50% proportion in the placebo arm used to justify sample size. The revised primary endpoint analysis will treat contusion volume as a continuous variable and assess the change in volume from baseline as a continuous variable; adjusted by imaging modality. Change in contusion volume at 24 hours was added as a secondary endpoint which will involve NCCT to NCCT comparison. The Day 180 GOS-E assessment will be favored over its Day ~~█~~ measurement as it is the registrational endpoint in TBI studies.

This change also affects Section 7.1, Study Overview; Section 11.4.2.1, Neurosurgical Intervention; Section 13.1, Clinical Efficacy Assessments; Section 16, Statistical Methods and Determination of Sample Size; Section 16.2.1, Analysis Population; Section 16.2.2.2, Analysis of the Primary Endpoint; Section 16.2.2.3, Analysis of the Secondary Endpoints; and Section 16.8, Sample Size Considerations.

CONFIDENTIAL

The information contained herein may not be used, disclosed, or published without the written consent of Biogen MA Inc.

Section 6, Study Objectives and Endpoints

Change:

[REDACTED] GOS-E at Day [REDACTED] replaced GOS-E at Day 180.

Now reads:

[REDACTED]

[REDACTED]

[REDACTED]

[REDACTED]

[REDACTED]

Rationale:

[REDACTED]

Section 7.1, Study Overview

Change: The database-lock language was changed to remove the Day 90 lock

Now reads:

~~The study database will first be locked after the last participant finishes their Day 4 Visit and the primary and imaging based endpoints will be analyzed. A final study database lock will occur when the last participant completes their Day 90 Follow-up Visit to analyze key functional outcomes. The long term follow-up database will be locked for evaluation of long term safety and efficacy after the last participant completes the Day 180 Follow-up Visit. The end of the study is when the last participant completes their Day 180 assessments.~~

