## 1. Introduction

This statistical analysis plan (SAP) provides details of all pre-planned statistical analyses for Study 252BN201 (protocol version 3.0). Any deviation to this SAP will be described in the Clinical Study Report (CSR).

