#### **3.4.1. Change in Total Contusion Volume (hematoma plus perihematomal edema) from Baseline to 96 Hours**

Total contusion volume will be assessed by the central imaging core laboratory on baseline NCCT, 24-hour NCCT, and the 96-hour scan (MRI and / or NCCT) and the scans obtained prior to DC, IPH evacuation or CMO. Change in total contusion volume (hematoma plus perihematomal edema) as measured by brain imaging from baseline to 96 hours or prior to DC, IPH evacuation, or CMO if these procedures occur before 96 hours per central review, will be derived from available central reads, at baseline (before Hour 0) and closest to Hour 96. If multiple timepoints

are applicable, the read from the visit closer to Hour 96 will be used for analysis. If both MRI and NCCT have been carried out then the MRI read will be used.

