### Sensitivity Analysis and Supplementary Analysis

- A supplementary analysis on the primary endpoint will be performed on the mITT population and excluding all DC, IPH evacuation or CMO.
- A sensitivity analysis on the primary endpoint will be performed on the PP population.
- A sensitivity analysis on the primary endpoint will be performed on the mITT population using the eCRF data as covariates rather than IRT stratification data.

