## **APPENDICES**

## APPENDIX 1. IMAGING DATA PER THE CENTRAL REVIEW

### *On-Protocol Images for the Central Review*

MR and NCCT images will be used to assess changes in brain contusion, hemorrhage and edema volume, [REDACTED]. Eligible participants will undergo NCCT at baseline and Hour 24 and MRI/NCCT at Hour 96.

- Screening NCCT will be the one closest to the randomization, which is assessed for eligibility with a brain contusion volume of > 3mL per investigator review and used for stratification at randomization
- All NCCT/MRI brain images collected by the imaging CRO up to the Hour 96 visit (or NSx or CMO, if earlier) will be considered on-protocol images and will be submitted for central review

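### The protocol's primary ANCOVA adjusts for 96-hour imaging modality; the SAP's does not, and SAP Section 6 lists no change

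*SAP*

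**What the plan says.** Protocol 16.2.2.2 specifies an ANCOVA adjusted for all stratification factors, "96 hours imaging modality (MRI vs NCCT) and baseline contusion volume per the central read".

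The SAP states in Section 1 that it covers protocol version 3.0, the version that contains this covariate. SAP 5.6.1 gives a single covariate set for all endpoint models: the IRT stratification factors, "baseline contusion volume per the central review and baseline GCS". SAP 5.6.2 refers the primary ANCOVA to that set and adds nothing. Its sensitivity and supplementary analyses are three: one excluding participants with DC, IPH evacuation or CMO, one in the per-protocol population, and one "using the eCRF data as covariates rather than IRT stratification data". SAP Section 6, which is meant for changes from the protocol's analyses, is marked not applicable.

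On the scans themselves, SAP Appendix 1 says: "Eligible participants will undergo NCCT at baseline and Hour 24 and MRI/NCCT at Hour 96". SAP 3.4.1 adds: "If both MRI and NCCT have been carried out then the MRI read will be used". Protocol Table 2 (footnote 14) accepts NCCT at Hour 96 for participants who cannot have an MRI.

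The version 3 amendment summary is cited here only for the sponsor's reasoning. It says that under the former binary endpoint the blinded expansion rate "appeared to be very high, particularly for participants with MRI scans at 96 hours", and that the revised analysis will "assess the change in volume from baseline as a continuous variable; adjusted by imaging modality".

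**The concern.** Baseline is always NCCT. The 96-hour value is MRI for some participants and NCCT for others, so the outcome pools cross-modality and same-modality changes. The sponsor recognised this when it revised the endpoint and attached modality adjustment as the safeguard. The SAP's model drops that safeguard without comment.

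The SAP's list matches the one protocol 16.2.2.3 uses for GOS-E, mRS and delayed intubation. Modality may have been lost when one list was applied to every model, but that is conjecture.

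At stake is a single prespecified primary test. With two written models, the choice between them could be made after unblinded results exist, including those of the interim analysis at about 90 participants (SAP 4.1), which covers the 96-hour volume change. The SAP has a same-modality comparison at 24 hours, but none is visible at 96 hours.

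**Working it through.** **Text comparison of the primary model**

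| Element | Protocol 16.2.2.2 | SAP 5.6.1 and 5.6.2 |
|---|---|---|
| Stratification factors | yes | yes (IRT) |
| Central-read baseline contusion volume | yes | yes |
| 96-hour modality, MRI vs NCCT | **yes** | **no** |
| Baseline GCS in addition to its stratum | not named | yes |
| Multiple imputation for missing Hour 96 values | yes | not mentioned |

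Modality does not enter by another route. The stratification factors (SAP 3.5.1) are contusion volume, GCS, age and region. The rule in SAP 3.4.1 selects a read when both scans exist, and selecting a read does not adjust for modality. The SAP's covariate sentence has no blacked-out text that could hide the term.

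**The plan's own power.** Inputs from protocol 16.8: SD 29 mL, difference 15 mL, 80 per pooled group, two-sided 0.05.

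- SE = 29 × √(2/80) = 4.585 mL
- Noncentrality = 15 / 4.585 = 3.271
- Noncentral t with 158 df: power 0.902, which reproduces the stated 90%

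**Effect of restoring modality.** The documents give neither the mean MRI-NCCT offset D nor the MRI share q. Assume D = 5 to 20 mL and q = 50% to 80%, and read 29 mL as the raw SD across both modalities. Then:

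- Adjusted SD = √(29² − q(1−q)D²). For q = 0.5 and D = 20: √(841 − 100) = 27.22 mL
- Equivalent N = 160 × 29² / SD²

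| q | D (mL) | Adjusted SD (mL) | Power | Equivalent N |
|---|---|---|---|---|
| 0.5 | 5 | 28.89 | 0.904 | 161.2 |
| 0.5 | 10 | 28.57 | 0.910 | 164.9 |
| 0.5 | 20 | 27.22 | 0.934 | 181.6 |
| 0.8 | 5 | 28.93 | 0.903 | 160.8 |
| 0.8 | 10 | 28.72 | 0.907 | 163.1 |
| 0.8 | 20 | 27.87 | 0.923 | 173.2 |

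If 29 mL is instead the within-modality SD, leaving modality out raises the SD to 29.1 to 30.7 mL. By the normal approximation, power then falls from 0.905 to between 0.904 and 0.871.

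**How often the two analyses disagree.** Simulation with 8000 trials per cell and total SD held at 29 mL compared a t-test with an ANCOVA containing modality.

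- The SD of the difference between the two estimates was 0.5 to 1.6 mL.
- With a true effect of 15 mL, the results fell on opposite sides of 0.05 in 1.2% to 4.8% of trials.
- With a true effect of 9 mL, they did so in 2.6% to 11.9%. That effect was chosen because it lies at the significance boundary: 4.585 × 1.975 = 9.06 mL.

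**Bias.** Chance imbalance in MRI share between arms is random error that the SE already carries. Bias would need a systematic difference in MRI use between arms. It would then equal the offset times the difference in share, for example 10 mL × 10 percentage points = 1.0 mL.

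**The case against.** Protocol Section 16 leaves final statistical details to the SAP, so the SAP may refine the model. Dropping modality can also be defended. It is determined after randomization and may depend on clinical condition, and if treatment affects who can have an MRI, conditioning on modality can itself bias the estimate. This has force, but the SAP gives no such reason, and removing a covariate the protocol names is the kind of change Section 6 exists to record.

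Section 6 may also be unfilled template text rather than a positive statement: Section 7 reads the same although the version history records a correction. It is therefore fairer to say that Section 6 lists no change than that the sponsor denied one. The mismatch remains.

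The size is a fair target. The upper figures need a 20 mL offset, larger than the 15 mL design effect, with a 50% MRI share. MRI is the default 96-hour scan, so the share could exceed 80%; at an assumed 90% and 10 mL, power rises only from 90.2% to 90.5%. The amendment's remark about MRI concerns the superseded binary endpoint and supplies no offset in mL. The simulation left out the other covariates, which both disputed models contain, so its rates are illustrative.

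Finally, redacted parts of the SAP might use modality in exploratory work, but that would not be the primary model.

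**Conclusion.** The concern holds. The protocol's primary model contains 96-hour modality, the SAP's does not, no listed sensitivity analysis covers it, and no departure is recorded. Confidence in this is high because it rests on the text alone.

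The statistical cost of omission is mainly avoidable residual variance and is probably modest: about 0.1 to 3.2 percentage points of power, equivalent to roughly 1 to 22 participants. These sizes depend on the assumed offset, the assumed MRI share and reading 29 mL as a raw SD. No bias is claimed unless MRI use differs systematically between arms.

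It is a must-fix because the primary hypothesis test has two written definitions that can disagree on significance. That this is a Phase 2 study without multiplicity control does not remove the need for one defined primary model.

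**What to change.** Amend SAP 5.6.2 before the Day 4 lock, for example: *The primary ANCOVA adjusts for the covariates in Section 5.6.1 plus the modality (MRI vs NCCT) of the scan that supplies the primary value, including a scan taken before DC, IPH evacuation or CMO.*

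In the same edit:

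- Reconcile the multiple imputation in protocol 16.2.2.2 with SAP 5.6.2. If it is kept, state how modality is set for imputed values, for example by imputing it in the same model.
- Reconcile the added baseline GCS term. The protocol's covariate wording is open enough to permit it, but the SAP should say so.
- Add a sensitivity analysis without modality, because modality is determined after randomization.
- Add a supportive NCCT-to-NCCT analysis where a 96-hour NCCT exists, labelled as a selected subset because that scan is optional alongside MRI (protocol Table 2, footnote 7).
- Tabulate MRI share by arm.

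If the sponsor prefers the model without modality, Section 6 should list and justify that departure, and a modality-adjusted sensitivity analysis should be kept. No change is asked for the 96-hour edema model, for which the protocol names no covariates.

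The cost is SAP wording, one degree of freedom and three short tables. No new data are collected.
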